15.0 Confidentiality, Privacy, and Data Security

15.1 PROTECTING PRIVACY: Indicate how subject privacy will be protected:

Conduct conversations about the research in a private room

Ask the subject how they wish to be communicated with – what phone numbers can be called, can messages be left, can they receive mail about the study at home, etc.

Take special measures to ensure that data collected about sensitive issues do not get added to their medical records or shared with others without the subject's permission

Other methods (describe below)

15.2 SENSITIVE DATA: Do any of the instruments ask about illegal or stigmatized behavior:

Yes No

IMPORTANT NOTE: Indicate in the consent form what kinds of sensitive information will be collected.

15.3 CONSEQUENCES OF A LOSS OF PRIVACY OR CONFIDENTIALITY: Could a breach of privacy or confidentiality result in any significant consequences to participants, such as criminal or civil liability, loss of state or federal benefits, or be damaging to the participant's financial standing, employability, or reputation:

Yes No

15.4 EXTRA CONFIDENTIALITY MEASURES: Explain any extra steps that will be taken to assure confidentiality and protect identifiable information from improper use and disclosure, if any:

Study ID #s will be created for each participant as an extra confidentiality measure, as it is an extra layer of protection for participants and does not link any PHI to the study data.

15.5 * REPORTABILITY: Do you anticipate that this study may collect information that State or Federal law requires to be reported to other officials, such as elder abuse, child abuse, or threat to self or others: (REQUIRED)

Yes No

The confidentiality and privacy section of the consent form should include this as a possible risk of participation.

* Describe the types of reportable information the research team may encounter and provide the details of the reporting plan: (REQUIRED)

At two separate time points during this study a questionnaire will be sent to participants to evaluate for signs/symptoms of Depression. At any point whether on questionnaire or on verbal report there is concern that a participant is at risk for becoming suicidal, this will be reported immediately (both in the patient's medical record and study file) and steps will be followed based on the Suicidal Ideation Protocol. To ensure the safety of the individual, [name] (clinical psychologist at UCSF) will be notified immediately so that further evaluation and management can be taken. A set of questions are available on the protocol to evaluate imminent risk of harm. Of note, the study file with the reported event will not contain the name or any identifying information of the participant.

15.6 CERTIFICATE OF CONFIDENTIALITY: Will this study obtain a Certificate of Confidentiality:

Yes No

15.7 SHARING OF RESEARCH RESULTS: Will there be any sharing of EXPERIMENTAL research test results with subjects or their care providers:

Yes No

15.8 * IDENTIFIERS: Will any personal identifiers be collected: (REQUIRED)

Yes No

Check all the identifiers that may be included:

- Names
- Dates
- Postal addresses
- Phone numbers
- Fax numbers
- Email addresses
- Social Security Numbers*
- Medical record numbers
- Health plan numbers
- Account numbers
- License or certificate numbers
- Vehicle ID numbers
- Device identifiers or serial numbers
- Web URLs
- IP address numbers
- Biometric identifiers
- Facial photos or other identifiable images
- Any other unique identifier

* Could study records include ANY photos or images (even 'unidentifiable' ones): **(REQUIRED)**

Yes No

15.9 DATA DISCLOSURE: Will identifiable information be shared with outside groups:

Yes No

15.11 * DATA COLLECTION AND STORAGE: (check all that apply): (REQUIRED)

Collection methods:

- Paper-based (surveys, logs, diaries, etc.)
- Electronic case report forms (CRFs), such as OnCore or another clinical trial management portal
- Web-based online surveys or computer-assisted interview tool
- Mobile applications (mobile or tablet-based)
- Wearable devices
- Audio/video recordings
- Other:

* What online survey tool will you use: **(REQUIRED)**

- Qualtrics (Recommended)
- RedCAP (Recommended)
- Survey Monkey (NOT recommended and may require UCSF ITS Security review)
- Other

* Data will be collected/stored in systems owned by (check all that apply): **(REQUIRED)**

- UCSF
- SF VAMC
- Amazon (Amazon Cloud)
- Other academic institution
- 3rd party vendor (business entity)
- Other (explain below)

15.12 DATA SECURITY: Indicate how data are kept secure and protected from improper use and disclosure (check all that apply): NOTE: Whenever possible, do not store subject identifiers on laptops, PDAs, or other portable devices. If you collect subject identifiers on portable devices, you MUST encrypt the devices.

- Data are stored securely in My Research
- Data are coded; data key is destroyed at end of study
- Data are coded; data key is kept separately and securely
- Data are kept in a locked file cabinet
- Data are kept in a locked office or suite
- Electronic data are protected with a password
- Data are stored on a secure network
- Data are collected/stored using REDCap or REDCap Survey
- Data are securely stored in OnCore

15.13

* **DATA SECURITY:** Confirm below that you will keep data confidential: (REQUIRED) I will keep any data sets that include identifiers secure and protected from improper use and disclosure by using methods such as:

- Physical Security – Keeping data in locked file cabinets, locked offices, locked suites, and physically securing computers and servers.
- Electronic Security – Following [UCSF minimum security standards for electronic information resources](#), which includes (but is not limited to): not storing identifiers on portable devices like laptops or flash drives if they are unencrypted, encrypting portable devices, and storing data in password-protected files and on secure networks.

Yes

15.15 HIPAA APPLICABILITY: Study data will be:

- Derived from the Integrated Data Repository (IDR) or The Health Record Data Service (THREDS) at SFGH
- Derived from a medical record (e.g. APeX, OnCore, etc. Identify source below)
- Added to the hospital or clinical medical record
- Created or collected as part of health care
- Obtained from the subject, including interviews, questionnaires
- Obtained ONLY from a foreign country or countries
- Obtained ONLY from records open to the public
- Obtained from existing research records
- None of the above

Unless a waiver of Authorization is granted, in addition to the consent form, participants will need to sign [UCSF Research Subject Authorization Form \(HIPAA Form\)](#). NEW REQUIREMENT - This form should be uploaded in the Other Study Documents section of the Initial Review Submission Packet Form. Failure to obtain HIPAA Authorization for research is one of the most common findings from QIU Routine Site Visits. Your IRB approval letter will include instructions about HIPAA requirements specific to your study.

If derived from a medical record, identify source:

APeX

15.16 * HIPAA - PERMISSION TO ACCESS SENSITIVE DATA: Does the research require access to any of the following types of health information from the medical record: (check all that apply) (REQUIRED)

- Drug or alcohol abuse, diagnosis or treatment
- HIV/AIDS testing information
- Genetic testing information
- Mental health diagnosis or treatment
- None of the above

Important note: Ensure that participants initial the corresponding line(s) in Section C of the HIPAA authorization form during the consent process.

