7.0 Research Plan and Procedures

7.1 This new consolidated section requests information about:

- Hypothesis
- Aims
- Study Design
- Background and Significance
- Preliminary Studies
- Procedures
- Statistical Methods
- References

Later sections include:

- Drugs and Devices
- Sample Size, Eligibility, and Subjects
- Recruitment and Consent
- Risks and Benefits
- Data and Safety Monitoring Plan
- Confidentiality, Privacy and Security
- Financial Considerations
- Qualifications of Personnel
- Other Approval and Registrations

7.2 HYPOTHESIS: Describe the hypothesis or what the study hopes to prove **(Help Text updated 9/13):**

We propose that patients with Polycystic Ovary Syndrome (PCOS) on a continuous 6 month active oral contraceptive (OCP) preparation (no placebo pills for 6 months straight) will have improved Testosterone suppression as compared to patients taking cyclical (monthly) OCPs, who may have rebound ovarian function during days 21-28 of their menstrual cycle when receiving sugar pills. With continuous OCP use we also hypothesize that patients will have improved clinical findings of hyperandrogenism (acne and hirsutism) compared to cyclic OCP users.

7.3 AIMS: List the specific aims:

1. To conduct a pilot feasibility study observing the use of 2 formulations of an OCP (continuous 168 day active hormone pills vs. cyclical 21 day active/7day placebo pill packs) in patients with Polycystic Ovary Syndrome (PCOS).
2. To determine the effect of 6 months of continuous (168 days of active hormone pills) vs. cyclical (21 day active and 7 day placebo pills) OCP therapy on biochemical findings of hyperandrogenism (Testosterone levels and free androgen index).
3. To determine the effect of 6 months of continuous (168 days of active hormone pills) vs. cyclical (21 day active/7 day placebo pills) OCP therapy on cutaneous findings of hyperandrogenism (male pattern hair growth also known as hirsutism and acne).
4. To determine the effect of 6 months of continuous (168 days of active hormone pills) vs. cyclical (21 day active/7 day placebo pills) OCP therapy on self reported symptoms of anxiety and /or depression as collected from validated questionnaires.

7.4 DESIGN: Briefly describe the study design (e.g., observational, interventional, randomized, placebo-controlled, blinded, cross-over, cross-sectional, longitudinal, pharmacokinetic, etc.):

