	Screening	Enrollment	1 month	3 months	(routine)
Questionnaires					
REDCap PCOS Multidisciplinary PCOS Clinic Pre-clinic Surveys (routine)	x				
REDCap Baseline Questionnaire		x			
REDCap 3 Month Follow Up Questionnaire /PCOS QOL				x	
REDCap 3 Month GAD-7 Questionnaire				x	
REDCap 3 month BDI-II Survey				x	
REDCap 3 Month Follow Up - Acne QOL Assessment				x	
REDCap 6 Month Follow Up Questionnaire /PCOS QOL					
REDCap 6 Month GAD-7 Questionnaire 2					
REDCap 6 Mond BDI-II Survey 2					
REDCap 6 Month Follow Up Questionnaire - Acne QOL Assessment					
REDCap 6 Month Follow Up Questionnaire - Hirsutism QOL Assessment					
Study Visits/Procedures					
Dermatologic Exam (mFG scoring)		x			
Pelvic Ultrasound		x			
Blood Work - Location	Patient's local lab - insurance covered	PCOS Clinic - study covers	PCOS Clinic - study covers	PCOS Clinic - study covers	Patient's local lab - insurance covered
Total Testosterone	x (routine)	*	†	†	
Free Testosterone	x (routine)	**			
Sex Hormone Binding Globulin	x (routine)	*	†	†	
LH	x (routine)	**	×		x
FSH	x (routine)	*	×		x
Estradiol	x (routine)	**	×		x
Fasting Lipid Panel	x (routine)	**			x
HbA1c	x (routine)	**			x
Fasting serum glucose	x (routine)	**			x
Insulin	x (routine)	**	†	†	
Email Reminders		x			x
* if initial screening blood work done at the patient's outside lab is obtained >2 months from start of study, these select labs will be sent from the PCOS clinic to the University of Virginia, Center for Endocrinology and Metabolism to establish accurate baseline values.					
** If the patient is a return patient to the clinic looking to reestablish care and participate with the study, all labs will be sent from the PCOS clinic to the University of Virginia, Center for Endocrinology and Metabolism to establish accurate baseline values.					
† indicates the select labs that will be sent from the PCOS clinic (where it is drawn) to the University of Virginia, Center for Endocrinology and Metabolism to establish accurate baseline values.					
Please refer to the attached study document "CCOUP Study Timeline" for the full procedure table.					

7.11 STANDARD CLINICAL PRACTICE: To what extent, if any, do the planned research procedures differ

from the care that people would otherwise receive at this institution or the study site if not being done locally:

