The REDCap database will also be utilized aside from accessing the participant's medical records. Prior to enrollment in this study, all patients who are seen at the UCSF PCOS Multidisciplinary clinic in Mission Bay or at the UCSF Center for Reproductive Health with a complaint of PCOS complete an online survey and questionnaire which includes concerns about hair growth, weight, eating, body shape and a psychological assessment. The study investigator will review both the EMR records and REDCap survey for each potential participant who may meet eligibility requirements for the study prior to their initial clinic visit.

11.3 DETERMINATION OF ELIGIBILITY: How, when, and by whom will eligibility for recruitment be determined:

New referrals to the PCOS Multidisciplinary clinic or the Center for Reproductive Health with a concern for PCOS will be screened by the study team or clinical investigator just prior to their initial clinic visit by reviewing their EMR (APeX) chart and REDCap pre-clinic surveys. A screening form (attached to this IRB) will be used to see if the patient meets eligibility criteria to be included in the study and will be completed by either the clinical research coordinator or clinical investigator either at the patient's initial referral visit or second visit, when they come for routine follow up. After the patient has been seen in clinic, diagnosed with PCOS, and meets eligibility requirements will we approach the patient about our study and obtain informed consent if interested.

11.4 * INITIATION OF CONTACT: Who initiates contact (check all that apply): (REQUIRED)

- Investigators/study team
- UCSF recruitment unit (e.g. CTSI Consultation Services)
- Potential participant
- Other (explain below)

11.5 * HOW IS CONTACT INITIATED: (check all that apply): (REQUIRED)

- In person
- Phone
- Letter / email
- Website or app
- Other (explain below)

Attach the telephone recruitment script in the Other Study Documents section of the Initial Review Submission Packet Form. If potential participants will initiate contact, attach the telephone screening script that will be used to provide more information about the study and determine if callers are eligible to participate.

Attach the recruitment letter or email template in the Other Study Documents section of the Initial Review Submission Packet Form.

11.6 RECRUITMENT PLAN: Based on the checkboxes you chose above, please provide a narrative describing your recruitment plan. We want to know:

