13.0 Risks and Benefits

13.1 RESEARCH-RELATED RISKS: Check if your study involves any of these specific research-related risks to participants that may need to be disclosed in the consent form:

- For interventional studies, risk that the regimen may be more harmful or less effective than other available interventions
- Risks associated with radiation exposure for imaging studies specifically for research purposes
- Risks associated with the administration of contrast agent for imaging studies
- Risks associated with withholding of treatment or discontinuation of current treatment (e.g., washout period is required by the study protocol)
- For randomized, placebo-controlled trials, possible temporary or permanent health consequences from the deprivation of effective therapies during the placebo administration period
- For studies involving a sham surgical procedure, the risk that participants may experience increased morbidity without the possibility of benefit
- Risks associated with modification or extension of a surgical procedure primarily for research purposes (e.g. risks associated with prolonging anesthesia, time in the operating room, etc.)
- Risk of pain or physical discomfort caused by the research intervention

Possible personal discomfort due to sensitive topics (stress, embarrassment, trauma)

13.2 RISKS: Describe any anticipated risks and discomforts not listed above:

Aside from the above mentioned risks, participants may be at risk for any of the number of adverse side effects that are seen with OCP therapy (listed below).

Likely side effects: Premenstrual syndrome (13.2%), headache/migraine (10.7%), breast pain/tenderness/discomfort (8.3%), nausea/vomiting (4.5%), abdominal pain/tenderness/discomfort (2.3%), mood changes (2.3%).

Less likely side effects: Gallbladder disease, hypertension, hepatic adenomas, elevation in lipid levels

Rare but serious side effects: Venous thromboembolism (risk is greatest during the first year of use and less than the risk associated with pregnancy), hepatocellular carcinoma. Women over 35 years of age who smoke have an increased risk of serious cardiovascular events from OCP use including heart attack, blood clots or stroke.

Side effects specific to Yasmin: There may be a slight increase incidence of Deep Vein Thrombosis (a very rare side effect of all OCPs) for Yasmin as compared to some other OCPs.

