Trial Stopping Rules: In the event that a rare but serious side effect such as a thromboembolism or hepatocellular carcinoma occurs within multiple subjects within a study group, the PI will investigate this adverse event (AE) to determine the safety of continuing the trial further. As this pilot study will be recruiting individuals over a long period of time, the PI and investigators will meet to discuss on an on-going basis patient AE to determine if there is a need to stopping the trial due to patient safety concerns.

A suicidal ideation and depression protocol has also been set in place in case a patient is found to have answered Question 9 of the BDI-II surveys with a score greater than zero or a total score over 19. The protocol details specific steps that need to be taken immediately including contacting [name] and following up with the patient immediately. Details of the protocol have been attached to this application as a separate document.

14.3 * DATA AND SAFETY MONITORING BOARD (DSMB): Will a Data and Safety Monitoring Board (DSMB) be established: (REQUIRED)

Yes
 No

Guidelines

A Data and Safety Monitoring Board (DSMB) or Data Monitoring Committee (DMC) is a formal, independent committee that is specifically established to conduct interim monitoring, oversight and analysis of study information and data to assure the continuing safety, efficacy, appropriateness, relevance,

and integrity of the study.

The UCSF IRB reserves the right to request a DSMB/DMC for any study. However, the following are factors that the IRB will consider when making this determination:

- There is a significant likelihood of a serious adverse event to subjects
- The study is conducted at multiple sites and the level of risk is greater than minimal
- The study generates data that are blinded or randomized
- The study involves a large number of patients randomized to one of two or more interventions
- A study for which the performance of an interim analysis is crucial for the protection of the subjects
- First use in humans
- First use in children
- The study involves gene transfer, stem cell therapy, or other novel interventions for which long-term outcome data are not known or available

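### Aim 4 compares regimens on anxiety and depression, but no baseline GAD-7 or BDI-II is named, so change, new onset and chance imbalance cannot be assessed on these scales

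*Combined protocol and SAP*

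**What the plan says.** Section 7.3 sets Aim 4 as the effect of six months of continuous versus cyclical pills "on self reported symptoms of anxiety and /or depression as collected from validated questionnaires".

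The Timeline in section 7.10 and the instruments list in section 7.12 name the two scales at follow-up only. The first anxiety form is "REDCap 3 Month GAD-7 Questionnaire" and the next is "REDCap 6 Month GAD-7 Questionnaire 2"; the BDI-II rows follow the same pattern. The procedures text in section 7.10 likewise places both at the month-3 and month-6 visits. Section 15.5 gives the count for depression: "At two separate time points during this study a questionnaire will be sent to participants to evaluate for signs/symptoms of Depression".

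Two forms come earlier. Section 11.2 describes a routine pre-clinic survey covering "weight, eating, body shape and a psychological assessment", and the Timeline has a REDCap Baseline Questionnaire at enrollment. The plan does not name the instruments in the first or describe the content of the second.

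For analysis, section 7.26 plans a chi-square between arms on anxiety and depression as categories. In the same paragraph, blood tests are compared with baseline and metabolic measures are likely to get a baseline-adjusted ANCOVA.

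**The concern.** By month 3 every woman has had about 12 weeks of pills, so the first named GAD-7 and BDI-II scores are post-treatment scores. In this open-label trial they are also reported after the woman knows her allocation. The planned chi-square counts a woman who was anxious before the study the same as one who became anxious during it.

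Four things are at stake for Aim 4:

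- Neither change from before treatment nor new onset can be estimated on these scales.
- With 30 women per arm, a chance difference in pre-existing symptoms can be neither seen nor adjusted for.
- Precision that a baseline covariate would give is lost.
- A woman who withdraws before month 3 contributes no Aim 4 score, and whether she had symptoms at entry is unknown.

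The plan takes baseline values for its blood tests and hirsutism score, so Aim 4 is treated less well than the other outcomes.

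**Working it through.** **1. Schedule, side by side**

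| Place | Before treatment | Month 3 | Month 6 |
|---|---|---|---|
| 7.10 Timeline, 7.12 | neither scale named | GAD-7, BDI-II | GAD-7 and BDI-II, both numbered 2 |
| 7.10 text | quality of life, acne and hair self-assessments | anxiety and depression screen; BDI-II on clinic day | the same |
| 15.5 | not mentioned | two depression time points in all | |

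The month-6 columns of the Timeline are not legible in the text, but the row labels carry the month. All these places agree that month 3 is the first named administration.

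**2. Inputs.** From the documents: 30 per arm (9.1, 9.3), 1:1 allocation (7.4), unadjusted chi-square (7.26). The plan gives no alpha, power, effect size or event rate for Aim 4, and 60 is a feasibility number, so there is no figure to reproduce. Assumed below: two-sided alpha 0.05, 80% power, no dropout, pre-treatment symptom prevalence p of 20–50%, baseline-to-follow-up correlation r of 0.3–0.7.

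**3. Is the planned comparison biased?** Simulation of 40,000 trials per setting with no treatment effect: 80% of women with symptoms at entry keep them, and 10% of the others develop them. At p = 20%, 30% and 50% the follow-up-only chi-square rejected in 4.9%, 4.7% and 5.1% of trials, with a mean between-arm difference of about 0. It is not biased.

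**4. Chance imbalance at entry.** Let X and Y be independent Binomial(30, p). A gap of 10 points is 3 women and a gap of 20 points is 6. The standard error of the gap is √(2p(1−p)/30); for p = 0.2 this is √(0.32/30) = 0.103.

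| p | SE of gap (points) | P(gap ≥ 10 points) | P(gap ≥ 20 points) |
|---|---|---|---|
| 0.2 | 10.3 | 0.417 | 0.075 |
| 0.3 | 11.8 | 0.481 | 0.120 |
| 0.4 | 12.6 | 0.510 | 0.147 |
| 0.5 | 12.9 | 0.519 | 0.155 |

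**5. Precision.** Comparing follow-up scores alone, the detectable difference is (1.96 + 0.84) × √(2/30) = 0.72 SD. Adjusting for the baseline score multiplies this by √(1−r²) and is worth 1/(1−r²) times the sample size.

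| r | Detectable difference (SD) | Power at 0.5 SD | Equivalent n per arm |
|---|---|---|---|
| no baseline | 0.72 | 49% | 30 |
| 0.3 | 0.69 | 53% | 33.0 |
| 0.5 | 0.63 | 61% | 40.0 |
| 0.6 | 0.58 | 68% | 46.9 |
| 0.7 | 0.52 | 77% | 58.8 |

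For r = 0.5, 1/(1−0.25) = 1.33; for r = 0.7, 1/(1−0.49) = 1.96. These gains apply to an analysis of scores. The planned chi-square takes no covariate, and its power at 30 per arm is 14% for 30% versus 20% and 39% for 40% versus 20% (assumed rates).

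**The case against.** **Validity.** A reader might infer that pre-existing symptoms cannot be separated from the treatment effect. The documents do not support that. Aim 4 is a contrast between two randomised arms, so pre-existing symptoms balance in expectation, and the test's error rate already allows for chance imbalance. Step 3 of the working bears this out.

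**Safety.** A reader might also infer that early mood harm would go undetected. The score trigger in section 14.2, "Question 9 of the BDI-II surveys with a score greater than zero or a total score over 19", indeed cannot operate before the first BDI-II. But section 15.5 acts on concern about suicide risk raised verbally at any time, section 13.3 provides for participants to report adverse reactions, and section 14.2 has a chart review every two weeks. A BDI-II before the first pill would still leave the interval up to month 3 uncovered. Both arms take the same drug and there is no untreated arm, so a before-after change common to both would mix drug effect with time, regression to the mean and clinic care.

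**Size.** It is tempting to scale the problem by the 2.3% rate of mood changes in section 13.2. That is an overall side-effect rate for the pill, not a difference between regimens, and says nothing about error in Aim 4.

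**A baseline may exist.** Section 7.10 says routine survey data will serve as baseline, and the wording in section 15.5 need not exclude a survey completed before enrollment. This stands as a caution: the supportable statement is that no GAD-7 or BDI-II baseline is named. Against it, both scales are separate named forms at follow-up with no counterpart earlier. Same-day BDI-II review is described only at months 3 and 6, and the survey content that section 7.10 lists as baseline omits anxiety and depression.

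**Importance.** This is the fourth aim of a pilot sized for feasibility. That limits the severity but does not remove the gap.

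**Conclusion.** The point holds in a limited form. No baseline on GAD-7 or BDI-II is named, and the Aim 4 analysis has no baseline term. The randomised comparison at months 3 and 6 remains valid in expectation. The loss is in change and new onset on these scales, in sight of chance imbalance, and in precision.

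The size rests on assumptions about prevalence and correlation that the documents do not supply. At a prevalence of 20–40%, there is a 7.5–14.7% chance of an unseen gap of 20 points or more at entry. At a correlation of 0.5–0.7, the forgone precision equals 1.33–1.96 times the sample size; at 0.3 the gain is small (power 49% to 53% for 0.5 SD). This is a worthwhile and cheap improvement, not a fatal flaw, but a pre-treatment score cannot be recovered for a woman once she has started pills.

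**What to change.** 1. **Sections 7.10 and 7.12:** add GAD-7 and BDI-II to the enrollment column and procedures text, completed on the clinic day before randomisation and first pill, with the same-day review and Suicide Ideation Protocol already used at months 3 and 6. If the pre-clinic survey or Baseline Questionnaire already contains both scales, say so and state when they are completed.
2. **Section 15.5:** change the number of depression time points from two to three.
3. **Section 7.26:** replace or supplement the chi-square with ANCOVA on the scores, or logistic regression if categories are kept, adjusted for the baseline score of the same scale.
4. **Women already enrolled:** keep them in the analysis with a missing-baseline indicator or mean imputation of the baseline. Whether the baseline was collected is settled before randomisation, so this does not bias the between-arm comparison, though these women bring little of the precision gain.

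The cost is an amendment, two REDCap questionnaires already in use, a few minutes per woman at enrollment, and some BDI-II triggers to handle that day under the existing protocol.
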